### H. Analytical Plan

Since this pilot study is primarily about feasibility, analysis will be limited. We will describe baseline characteristics including demographics and cardiometabolic risk factors by CGM metrics. We will use mixed models with a random subject effect to estimate change in glucose metric variables across follow up with adjustment for demographics and other relevant confounders of dysglycemia. We will assess differences in CGM metric changes between participants receiving the MTM intervention and controls with independent sample t-tests. We will conduct similar analysis for change in weight.

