#### Inclusion Criteria

• Demographics: Women 18 years of age and older who reside in Forsyth County, NC

- Pregnancy: Currently 24 or more weeks into a singleton pregnancy or who have given birth within the past 14 days
- Clinical evidence of GDM defined as either:
  - 3-hour oral glucose tolerance test (OGTT) results obtained in the second trimester of pregnancy that show at least 2 abnormal values in any of the following combinations:
    - Fasting glucose > 95 mg/dL and 1h > 180 mg/dL
    - Fasting glucose > 95 mg/dL and 2h > GE 155 mg/dL
    - Fasting glucose > 95 mg/dL and 3h > 140 mg/dL
    - 1h > 180 mg/dL and 2h > 155 mg/dL
    - 1h > 180 mg/dL and 3h > 140 mg/dL
    - 2h > 155 mg/dL and 3h > 140 mg/dL
  - A diagnosis of "gestational diabetes" included on the Problem List in Wake One during current pregnancy, regardless of OGTT values
- Pre-gravid overweight or obesity or excessive GWG: Overweight or obese (BMI ≥25.0 kg/m^2) prior to current pregnancy OR most recent weight exceeds predicted weight gain for current weeks gestational age based on starting BMI defined as:
  - Pre-pregnancy BMI of 30 kg/m^2 or more and weight at most recent clinical visit 20+ pounds over pre-pregnancy weight
  - Pre-pregnancy BMI of 25-29.9 kg/m^2 and weight at most recent clinical visit 25+ pounds over pre-pregnancy weight
- English Proficiency: Able to read/understand English at or above a level sufficient to comprehend recruitment, informed consent, and intervention materials.
- Access to a smart phone/tablet/computer capable of connecting to video calls or teleconferencing software.
- Access to freezer space to store 10 frozen meals delivered to the home each week.
- Willingness to Accept Treatment Assignment: Prospective participants must be willing to accept assignment to either the medically tailored meal intervention or the comparison intervention condition.

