#### E. Screening and Enrollment

We will generate weekly datasets using the Clarity reporting relational database in WakeOne to identify potentially eligible women within the electronic health record (EHR). The EHR data pulls will identify women, age 18 years or older, in their third trimester of pregnancy seen for obstetric care in a WFBH clinic in the past week who had a diagnosis of GDM with excessive GWG, and for whom English is the documented primary language. Datasets of up to 50 women who meet these criteria will be output weekly to a secure folder on the PHS network which only IRB-approved study staff may access. Datasets will also include patient name, age, MRN, expected delivery date, pre-gravid height and weight (to calculate BMI), current weight, diagnosis of GDM, and OGTT results. Research staff will then access individual EHR data to identify contact information and will place a telephone call to potential participants to discuss the study and to assess additional eligibility criteria. As we anticipate that some women who meet eligibility criteria may not appear in these datasets until very close to their expected delivery date and may not be reached for recruitment pre-partum, we will also attempt to contact women who appear in the dataset who have recently given birth (within the past 14 days). Additionally, a physician investigator will review diagnostic codes associated with recent encounters for all potential participants to identify any potential diagnoses or health conditions that may make participation unsafe or increase risk, including diagnosis of Type 1 or Type 2 diabetes pre-pregnancy, cardiovascular disease, essential hypertension, and dyslipidemia.

Potential participants who 1) satisfy the inclusion/exclusion criteria previously described, and 2) indicate that they are willing to provide written informed consent will be invited to complete a virtual baseline visit and be enrolled in the study. Informed consent will be obtained at the beginning of this visit (see Section I.b. Informed Consent for details). Given current patient volumes, we anticipate recruiting 1-2 women per week over a period of 3-4 months. As the study timeline is brief, 20

participants will be recruited into a MTM treatment group to ensure the feasibility of the intervention approach is tested. If sufficient time remains, an additional 10 participants will be recruited into a usual care comparison condition.

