After enrollment, participants will be routinely monitored via the EHR to determine when they are admitted for delivery and to check for any potential problems during the delivery. To standardize anticipated contacts across all participants, the Estimated Date of Delivery (EDD) will be used to schedule meal deliveries, mailings, and email contacts for both treatment groups. Our plan is to initiate participant data collection post-partum within 2 weeks of delivery. Study staff will contact the participant approximately one week after the EDD to check on delivery status. We will also collect contact information during the enrollment process for an alternative contact person in

Table 1. Outline of Weekly Video Emails

Week	Video
1	The 4th Trimester (St. Louis Children's Hospital video)
2	HELP -Mindfulness
3	HELP - ABCs of emotions
4	Phone visit with study team (no email)
5	HELP - Tipping the calorie balance
6	HELP - Healthy Eating
7	HELP - More About Healthy Eating
8	Phone visit with study team (no email)
9	HELP - Physical Activity 101
10	HELP - Problem solving
11	HELP - Creating an environment for success
12	Phone visit with study team (no email)

the case of negative outcomes during or after delivery. Study staff will make at least five (5) attempts by phone, email, or text message to reach enrolled participants or their alternate contacts in the 2 weeks following the EDD. Continuous glucose monitors, readers, daily diaries, digital scales, and informational materials about the study and healthy diet resources will be delivered to participants by mail after the participant has been reached and continued participation is

confirmed. Those participants who do not respond to study contact after delivery

or who decline further participation will not receive study-related materials or meal delivery and will be considered as drop-outs. For those participants who are recruited and enrolled after giving birth, data collection will begin from the date of recruitment and informed consent.

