### G. Measures

Measures in this study have been selected to reflect the feasibility, acceptability, and preliminary effectiveness objectives of this pilot study and include participant self-reported constructs, existing medical history and pregnancy history information from the EHR, and data collected directly via CGM. A table outlining the time points at which each measure is collected and the mode of collection is included in Table 3.

Demographics: We are collecting self-reported data on gender, race, ethnicity, highest level of education, marital status, and the number of adults and children living in the home.

Continuous Glucose Monitoring: Participants will wear a blinded FreeStyle Libre Pro CGM at baseline (first 2 weeks after delivery) and at follow up (after 3 months). CGM devices will be mailed to participants and a member of the study team will video call participants to provide instructions and real time guidance on attachment and activation of the CGM. In order to facilitate collecting baseline post-partum CGM data and weight, this call will occur as close to the actual date of delivery as is possible. The participants will wear the CGM for 14 days at the beginning (initial month) and end (3 months) of the study. They will also keep a daily diary of the timing of meals, sleeping, and exercise (Appendix C). Study staff will call participants on day 14 to remind them to remove the sensor and provide instructions and guidance if needed for removal. At the conclusion of the 3 months, an abbreviated remote virtual visit to aid in placement and activation of the second continuous glucose monitor will be conducted. Participants will return the continuous glucose monitors, readers, and daily diaries to the study coordinator by mail using prepaid mailers. A 1-page report with a summary of the 14-day glucose data (graph of glucose values with information on the normal range) will be provided back to participants together with a cover letter for them to share with their health care provider if they choose.

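### The only stated MTM v control comparison is an unadjusted t-test on change between groups filled in sequence; consider a baseline-adjusted estimate beside it

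*Combined protocol and SAP*

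**What the plan says.** Section III.H gives two analyses of the CGM metrics. The first concerns change over time: "We will use mixed models with a random subject effect to estimate change in glucose metric variables across follow up with adjustment for demographics", and for further confounders of dysglycemia that are not listed. No treatment term is stated. The second is the arm comparison: "We will assess differences in CGM metric changes between participants receiving the MTM intervention and controls with independent sample t-tests". No covariates are attached to it. For weight the plan adds only "We will conduct similar analysis for change in weight".

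Section III.E says how the arms are formed. Twenty women go to MTM, and then: "If sufficient time remains, an additional 10 participants will be recruited into a usual care comparison condition". The inclusion criteria do speak of assignment ("Prospective participants must be willing to accept assignment to either the medically tailored meal intervention or the comparison intervention condition"), but the text describes no randomisation. Figure 1 is not shown in the copy reviewed.

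On timing, III.G places the first sensor in the two weeks after delivery and, a few lines later, in the opening month. III.E schedules contacts from the estimated delivery date and mails the devices only once the woman has been reached. For late recruits, "For those participants who are recruited and enrolled after giving birth, data collection will begin from the date of recruitment and informed consent". The interval from delivery to first sensor can be derived: "participants will be routinely monitored via the EHR to determine when they are admitted for delivery", and the Appendix C diary asks for the placement date.

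**The concern.** Without randomisation the arms may differ at baseline in ways that affect change. The plan accepts that confounders of dysglycemia matter, because it adjusts its change-over-time model. As written, that adjustment does not reach the one contrast in which arms are compared.

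Section I.B says that metabolic disturbances of pregnancy resolve or persist within 12 weeks of delivery, so the baseline is measured while the metric may still be moving. Section II names 3-month CGM change as the primary measure of preliminary effectiveness, and III.D says the pilot's estimates will help design the powered trial. A reader given one unadjusted difference cannot tell how much of it reflects meals and how much reflects who was recruited when.

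**Working it through.** The plan gives no power or precision figure to reproduce. Below, SDs at each visit are set to 1, and r is the baseline/follow-up correlation. The documents give neither r nor any drift or timing difference, so these are assumptions.

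**1. Order of recruitment.** 20 + 10 = 30. At 1 to 2 women per week for 3 to 4 months (13 to 17.3 weeks), accrual is 13 to 35. Reaching 20 takes 10 to 20 weeks and reaching 30 takes 15 to 30. Controls come last and may not be recruited.

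**2. Would a group term in the mixed model be enough?** Write y(i,t) = a + b·time + g·group + d·group×time + h·x + u(i) + e(i,t), with x constant over time. For a woman with both visits, y(i,1) − y(i,0) = b + d·group + e(i,1) − e(i,0). Both x and u(i) cancel, so the estimate of d is the difference in mean change. In 12 simulated complete datasets the two agreed to within 1e-14. Adding an x-by-time term moved the estimate.

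**3. Precision of the written test at 20 v 10.** SE = √[2(1 − r)(1/20 + 1/10)] and t(28 df) = 2.048.
- r = 0.3: SE 0.458, half-width 0.94 SD
- r = 0.5: SE 0.387, half-width 0.79 SD
- r = 0.9: SE 0.173, half-width 0.35 SD

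**4. What baseline adjustment changes.** With c = 0.15, n = 30, q covariates and a systematic baseline difference D, the variance ratio (adjusted/change) is (1 + r)/2 × [1 + (q + D²/c)/(n − 3 − q)]. For q = 1:

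| r | D = 0 | D = 0.5 SD |
|---|---|---|
| 0.3 | 0.675 | 0.717 |
| 0.5 | 0.779 | 0.827 |
| 0.7 | 0.883 | 0.937 |
| 0.9 | 0.987 | 1.047 |

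Break-even is r = 0.93 and 0.81 respectively. If a share k of D would persist without meals, bias is (k − 1)D for the change score and (k − r)D for the adjusted estimate. At D = 0.5 and r = 0.5:
- k = 1 (stable): 0 v +0.25
- k = r (regression to the mean): −0.25 v 0
- k = 0 (transient): −0.50 v −0.25

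Neither method is better in every case.

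**5. Timing, no meal effect.** Assume one arm's first sensor is 7 days later on average and the metric drifts 0.05 SD per day. Sizes only:
- Follow-up fixed from delivery: change score 7 × 0.05 = 0.35 SD. With baseline adjustment only, r × 0.35 ≈ 0.17 at r = 0.5.
- Follow-up moves with the start, constant drift: change score 0.35 − 0.35 = 0. Baseline adjustment only, (1 − r) × 0.35 ≈ 0.17.
- Follow-up moves, drift fades. Assume a rate of 0.05·exp(−t/28), with 28 days a third of 12 weeks, and mean starts at days 7 and 14. The baseline gap is 1.4(e^−0.25 − e^−0.5) = 0.241. Twelve weeks later (days 91 and 98) it is 1.4(e^−3.25 − e^−3.5) = 0.012. The change-score bias is 0.23 SD.

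With follow-up fixed, a 3-day gap at 0.02 SD per day gives 0.06 SD.

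**6. Price of a timing term.** Take r = 0.5, a 7-day gap and a timing SD of 4 days, so the gap is 1.75 SD. With q = 2, the variance is (1 − r²)c × [1 + (2 + 1.75²/0.15)/25] = 0.75 × 0.15 × 1.897 = 0.213, so SE = 0.46 against 0.39 for the change score. With follow-up fixed, simulated root-mean-square errors were:

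| Drift (SD/day) | t-test | Baseline only | Baseline + timing |
|---|---|---|---|
| 0.02 | 0.41 | 0.35 | 0.46 |
| 0.05 | 0.53 | 0.39 | 0.46 |

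The timing term loses to the t-test at the low drift and to baseline-only adjustment at both.

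**The case against.** The strongest reply is that the harm from timing is hypothetical. Section III.E applies the same scheduling to both groups, so variation between women is built in but a difference between arms is not. The upper figure is also strained. An SD of 4 days is about a uniform spread over 14 days. Moving one arm by 7 days gives starts up to day 21, which fits only the wider of the two baseline windows in III.G. Constant drift of 0.05 SD per day would be 0.05 × 84 = 4.2 SD over 12 weeks. If the second sensor is dated from each woman's start, constant drift cancels in the t-test. All of this stands.

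It can also be said that III.H does not bar a group term or covariate-by-time terms, and that step 2 needs complete pairs, while CGM completion is itself a feasibility outcome. That stands too: the point is what the text states, and a clarifying sentence would settle much of it. Finally, III.H says that analysis will be limited, and III.D says the study is not powered for any outcome. That lowers the priority. It does not explain why the one arm comparison goes without the adjustment that the plan applies elsewhere.

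A reader might infer that the t-test is wrong, that the arms will differ in sensor timing, or that the pilot's group difference will set the next trial's effect size. The documents support none of these. Step 4 shows conditions under which the change score is the unbiased choice, no arm-specific timing mechanism is described, and III.D does not say that the group difference will be used in that way.

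**Conclusion.** The point holds as a cheap improvement to consider, not a required correction. As stated, the sole MTM v control comparison is unadjusted, the confounder adjustment is elsewhere, and adding only a group-by-time term with main-effect covariates would leave the difference unchanged when pairs are complete. Because the arms are filled in sequence with no randomisation described, a second estimate would show how sensitive the result is to baseline differences.

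The gain is modest. At 20 v 10 with no systematic baseline difference, baseline adjustment cuts variance by 32% at r = 0.3 and 1% at r = 0.9. With D = 0.5 SD the cut is 28% at r = 0.3, and there is a 5% loss at r = 0.9. Timing bias is a possibility of about 0 to 0.35 SD under the assumed 7 days and 0.05 SD per day. Its size turns on the follow-up anchor and the shape of the drift, so timing belongs in a sensitivity analysis.

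**What to change.** If controls are recruited:
- Keep the difference in mean change with its 95% CI. Beside it, report a regression of the 3-month CGM metric on group and the baseline value of the same metric, also with a 95% CI. Do likewise for weight.
- As a sensitivity analysis, add days from delivery to first sensor placement (or to the first weighing).
- Tabulate that interval, and the interval from delivery to follow-up, by arm.
- Label the comparison non-randomised, and say that neither estimate is guaranteed unbiased.
- State whether group enters the mixed model. If it does, add covariate-by-time terms, since main effects alone do not adjust the change.
- Reconcile the two baseline windows in III.G, and state whether follow-up is dated from delivery or from each woman's start.

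The cost is a few sentences and no new data. The regression uses one degree of freedom more than the t-test, or two with timing, and there is a second estimate to report. Precision falls if r is high or the arms differ in timing. One limit remains: III.F.a and III.G allow meals to start during the 14-day baseline wear. If that happens, the MTM baseline is partly measured on meals. Either analysis may then be biased, and conditioning on that baseline and on timing could add to the bias.

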#### I. Data Management

Case report forms and interviewer-administered questionnaires will be collected on paper and will be reviewed for completeness and accuracy in real time by the study staff during the visit. These forms will then be data entered by the study team member. Participant self-administered questionnaires will be emailed directly to the participant for completion prior to each data collection visit. We will use the Research Electronic Data Capture (REDCap) system for secure, web-based data entry and management. Use of the REDCap system allows real-time monitoring and reporting of study accrual, data collection, and retention rates. If needed, data can be securely downloaded directly by study team members for use in analyses. All data will reside securely within REDCap, and will not be linked to any other servers or analytic programs.

Electronic data are managed centrally, with a feedback mechanism through e-mail and web-based reporting. After reviewing forms for gross errors and missing data, study staff enters data from case report forms and interviewer-administered questionnaires through a web browser. No electronic data are housed locally, but automated data reports are available for the staff to request on-line. Validation checks are applied during the data entry process. These checks include intra- and inter-form checks for consistency of responses, range checking, and checks for required fields and skip patterns.

Participants will be enrolled and assigned IDs through the REDCap interface. Once inclusion and exclusion criteria are verified and the informed consent is completed, study staff will enroll participants and receive IDs immediately. Data collection and participant status will be tracked with a web-based interface.

The REDCap data management system will also provide confidentiality and data security. A very high level of data encryption during transmission (128 bit) coupled with the use of IDs, rather than subject names, provides adequate data security. The use of text containing identifying information is avoided.

### J. Human Subjects Protection

Potential risks to participants due to the proposed research are minimal. The medically tailored meals will be designed in consultation with a dietitian from the Endocrinology Department to follow American Diabetes Association guidelines and be appropriate for the initiation and maintenance of breastfeeding. Continuous glucose monitoring systems are considered minimally invasive, involving a sensor probe placed in the subcutaneous tissue to measure glucose levels in the interstitial fluid, with risks primarily including infection at device insertion site and skin irritation from tape used to secure the device.

Setup and removal of the continuous glucose monitors will happen with real time virtual support and guidance from a highly trained study coordinator. [name] is a practicing endocrinologist with extensive experience managing continuous glucose monitor devices. He will supervise the continuous glucose data collection and assess each resulting report for safety concerns. If necessary, he will contact participants directly with results that indicate the need for medical follow up; However, there are no alerts as the data are not available in real-time and the data collected are not clinically actionable at the time of the data download.

The investigators for the proposed research will receive only de-identified data and will have no contact with participants unless necessitated by participant need. This study poses minimal risk of loss of confidentiality for participants, but we will use data safety best practices to ensure that participant data remain secure and confidential.

### a. Subject Recruitment Methods

Participants will be screened for eligibility through the Obstetric Department at Wake Forest Baptist Health by obtaining a list of eligible patients from the EHR. The study coordinator will call potential participants to confirm eligibility and determine interest in volunteering for the study. All communication between the study coordinator and potential participants will be kept strictly confidential. Any information obtained during recruitment and screening from individuals who decline to participate will be destroyed at the end of the study.

### b. Informed Consent

Informed consent will be obtained remotely for all participants. We will use a Zoom (or other web-based platform) meeting to perform web-based informed consent. At the outset of the consent meeting, we will email prospective participants a link to a pdf version of the informed consent document. We will ask them to share their screen and open the consent form, which we will review with them, reviewing all required elements of consent, the content of the study, assessing for understanding and answering any questions they have. If the participant requests additional time to review the consent form, we will schedule a follow-up meeting as needed for signing. In order for weight to be measured remotely, we are planning to provide participants with a digital scale that will be used to transmit weight measurements directly to Carium, Inc., an internet-based platform used in the clinical setting to deliver telehealth or remote patient monitoring. In order to link the digital scale to a specific participant. Only the study identification number will be registered to link the scale; no identifying information for participants will be provided to Carium. The consent form includes information on the digital scale and Carium website. We have also included an option for participants to receive study communication via SMS text message in the consent form.

Once that process is complete, we will ask the participant to sign the consent document using the "pencil" function in their iPhone or computer's pdf viewer, save the signed copy and email it back to our research staff.

At that point, the staff member will also sign and date the consent form, and save the form with both signatures in the study folder on the secure network drive to which only IRB-approved study staff have access. A copy of the signed consent will also be emailed or printed and mailed (participant preference) to the participant for their records.

